9.0 Study Drug Exposure and Compliance

The duration (days) of study drug exposure and treatment compliance (%) will be summarized using descriptive statistics.

Study drug exposure will be calculated as follows:

ADA exposure in Study M10-870 = last dose date of ADA in Study M10-870 – first dose date of ADA in Study M10-870 + 14 days

Overall ADA exposure in Study M11-290 & Study M10-870 = ADA exposure in Study M10-870 + Overall ADA exposure in Study M11-290 (see Study M11-290 SAP)

Treatment compliance (%) is defined as the number of study drug injections received divided by the number of injections planned.

10.0 Efficacy Analysis

[figure not shown]
10.1 General Considerations

No confirmatory testing for efficacy endpoints will be performed in this open-label study.

[figure not shown]
Endpoints that are of the binary type will be analyzed as proportions including 95% CIs. Endpoints that are of the continuous type will be analyzed as changes from baseline, and reported including 95% CIs. OC and LOCF (see Section 6.0) will be used, unless otherwise noted.

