An x-ray of the wrist for the assessment of bone age will be obtained at Baseline; Weeks 48, 96, 144, 192, 240 and 288 visit to determine changes in bone maturation. Sites should use the Greulich and Pyle method for reading the x-ray.²¹ The x-ray report requires the signature of the radiologist who read the films. The bone age that is determined by the x-ray should be recorded on the eCRF. Assessment of bone age will not be required for subjects at the Premature Discontinuation visit.

The x-ray collected at the Week 52 visit of Study M11-290 will be used for the Baseline assessment (prior to receiving study drug). If the height velocity is 0 and, in the opinion of the investigator, a subject is no longer growing, the x-ray for bone age can be omitted.

[figure not shown]
Anthropometric Evaluations

Height and weight obtained at Baseline, Weeks 24, 48, 72 and 96, 144, 192, 240 and 288/Premature Discontinuation will be used by AbbVie Data Management and Statistical groups for determination of BMI and "z" score (observed height velocity [cm/yr] – mean height velocity for age and sex [cm/yr]/SD of the mean) for height.

At Baseline, height from the Week 52 visit of Study M11-290 will be used and maximal weight attained will be recorded.

Tanner Stage

Tanner Stage will be assessed at Baseline, Weeks 48, 96, 144, 192, 240 and 288/Premature Discontinuation Visit. Tanner Staging should be captured on the appropriate eCRF page. The Tanner Stage assessed at the Week 52 visit of Study M11-290 will be used for the Baseline assessment (prior to receiving study drug).

Pediatric Ulcerative Colitis Activity Index (PUCAI)

A PUCAI score will also be calculated at all study visits beginning at Baseline. The PUCAI score calculated at the Week 52 visit of Study M11-290 will be used for the Baseline assessment (prior to receiving study drug).

An example of the PUCAI is located in Appendix C.

[figure not shown]

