All time points and corresponding time windows are defined based on Rx days. The protocol specified visits and corresponding time windows are presented in the table below. Measures will only be displayed at the visits where they were planned to be measured. For example, Mayo score is collected at Weeks 0, 48, 96, 192 and 288/Premature Discontinuation (dependent on availability of optional endoscopy data at these timepoints).

Assigned Visit	Nominal Day	Time Window (Rx Day Range)
Week 0	1	≤ 1
Week 4	29	2 to 43
Week 8	57	44 to 71
Week 12	85	71 to 127
Week 24	169	128 to 211
Week 36	253	212 to 295
Week 48	337	296 to 379
Week 60	421	380 to 463
Week 72	505	464 to 547
Week 84	589	548 to 631
Week 96	673	632 to 715
Week 108	757	716 to 799
Week 120	841	800 to 925
Week 144	1009	926 to 1093
Week 168	1177	1094 to 1261
Week 192	1345	1262 to 1429
Week 216	1513	1430 to 1597
Week 240	1681	1598 to 1765
Week 264	1849	1766 to 1933
Week 288	2017	1934 to 2101

If more than one assessment is included in a time window the assessment closest to the nominal day should be used. If there were more than one observation with equal distance to the nominal day the latest one will be used in analyses. For any given variable, if more

than one measurement exists for a subject on the same day, the average of the measurements will be considered to be that subject's measurement for that day.

Missing Data Handling

In general, missing Baseline and safety data will not be imputed.

Baseline Value is Missing:

Subjects will be excluded from analysis of change from Baseline if Baseline evaluation is missing.

Missing Efficacy and Outcome Evaluations:

The following methods will be used for imputing missing values to perform the efficacy analyses.

[figure not shown]
For interim analyses, missing values will only be imputed up to the timepoint a patient could have potentially reached at the data cutoff for analyses.

Observed Cases (OC): missing values will not be used for the observed case analysis.

Last Observation Carried Forward (LOCF): For categorical and continuous efficacy variables the following rules will be used for LOCF approach:

- Baseline and pre-baseline values will not be used to impute the missing post-baseline values, and
- Missing values after baseline will be imputed using the last non-missing values after baseline and prior to the missing value.

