4. WPAI

The WPAI was developed to measure the effect of disease on productivity at work and its impact on daily activities. The questions ask about the impact of disease to the patient's caregiver within the past 7 days. Six questions asked on this questionnaire can be described briefly as follows:

Questions:

- Q1. Currently employed (working for pay)? (Yes/No)
- Q2. Hours missed from work due to PROBLEM.
- Q3. Hours missed due to other reasons.
- Q4. Hours actually worked.
- Q5. Degree PROBLEM affected productivity while working.
- Q6. Degree PROBLEM affected regular activities other than job.

WPAI scores are expressed as *percent impairment* based on the above questions. The four main impairment measures or scores are derived as follows:

Scores:

S1. *Absenteeism*: Percent work time missed due to PROBLEM:

$$100 \times \left[\frac{Q2}{O2 + O4} \right]$$

S2. **Presenteeism**: Percent impairment while working due to PROBLEM: $100 \times \left[\frac{Q5}{10} \right]$

S3. Percent *overall work impairment* due to PROBLEM:

$$100 \times \left[\frac{Q2}{Q2 + Q4} + \left\{ 1 - \frac{Q2}{Q2 + Q4} \right\} \times \frac{Q5}{10} \right]$$

S4. Percent *activity impairment* due to PROBLEM: $100 \times \left[\frac{Q6}{10} \right]$

5. Other

Body Mass Index (BMI, in kg/m²) will be obtained as:

 $BMI = weight (kg)/(height [m] \times height [m])$

"z" score for height velocity will be obtained as: (Observed height velocity [cm/yr] – mean height velocity for age and sex [cm/yr]/[SD of the mean]). NOTE: The mean and Standard Deviation (SD) will come from published table values: The CDC Growth Charts webpage of the Center for Disease Control and Prevention with derivation details on the "z" score:

[figure not shown]
http://www.cdc.gov/growthcharts/percentile_data_files.htm, STATAGE.xls ('stature-for-age-chart,' for height) to be used.

Inappropriate Tanner stage will be defined depending on age and sex as follows: $girls \ge 14$ years/boys ≥ 15 of age with a Tanner stage of 1; $girls \ge 16$ years/boys ≥ 18 of age with a Tanner stage < 4; $girls \ge 19$ years/boys ≥ 19 of age with a Tanner stage of < 5.1.

7.0 Demographics, Baseline Characteristics, Medical History, and Previous/Concomitant Medications

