10.2 Efficacy Analysis

The efficacy endpoints are:

- The proportion of subjects who achieve clinical remission as measured by PMS (defined as a PMS ≤ 2 and no individual subscore ≥ 1) over time;
- The proportion of subjects who achieve clinical response as measured by PMS (defined as a decrease in PMS ≥ 2 points and ≥ 30% from Study M11-290-Baseline) over time;
- The proportion of subjects who achieve PUCAI remission (defined as < 10) over time;
- The proportion of subjects who achieve PUCAI response (defined as a decrease in PUCAI ≥ 20 points from Study M11-290-Baseline).
- Change from Baseline in total IMPACT III Quality of Life score and subscores over time for subjects at least 9 years old at Baseline;
- Change from Baseline in WPAI scores over time;
- Change from Baseline in "z" scores for height over time;
- Change from Baseline in BMI over time;
- Change from Baseline in "z" scores for weight-for-age over time;
- Change from Baseline in albumin and total protein over time;
- Change from Baseline in hemoglobin, hematocrit, red blood cell count over time;
- Change from Baseline in hs-CRP levels over time;
- Proportion of subjects at appropriate Tanner stage (see Section 6.0) over time;
- Proportion of subjects in Mayo score clinical response over time (for subjects with available Mayo score);
- Proportion of subjects in Mayo score clinical remission over time (for subjects with available Mayo score);
- Proportion of subjects who achieve mucosal healing over time as measured by Mayo endoscopy subscore (defined as ≤ 1, for subjects with available Mayo score)
- Proportion of subjects in 9 point Mayo score (without PGA) clinical remission over time (for subjects with available Mayo score);

• Proportion of subjects in 6 point Mayo score (without PGA and endoscopy subscore) clinical remission over time (for subjects with available Mayo score).

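### SAP 10.1 carries the age-dependent Tanner endpoint forward by LOCF with no time cap at the final analysis, so unexamined adolescents are judged against an age limit they have passed

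*SAP*

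**What the plan says.** SAP 10.1 plans both observed cases and LOCF for efficacy endpoints ("OC and LOCF (see Section 6.0) will be used, unless otherwise noted") and attaches a 95% confidence interval to each proportion. SAP 10.2 lists "Proportion of subjects at appropriate Tanner stage (see Section 6.0) over time" and notes no exception.

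The LOCF rules are in SAP 6.0, Missing Data Handling:

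- Scope: "For categorical and continuous efficacy variables the following rules will be used for LOCF approach".
- Rule: "Missing values after baseline will be imputed using the last non-missing values after baseline and prior to the missing value".
- Baseline is not carried: "Baseline and pre-baseline values will not be used to impute the missing post-baseline values".
- The only limit on how far a value is carried concerns interim analyses: "For interim analyses, missing values will only be imputed up to the timepoint a patient could have potentially reached at the data cutoff for analyses". No limit is set for the final analysis.

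SAP 6.0, Score Definitions, item 5 (Other), makes the classification age-dependent: "Inappropriate Tanner stage will be defined depending on age and sex as follows". A girl fails at stage 1 from age 14, below stage 4 from 16 and below stage 5 from 19. For a boy the ages are 15, 18 and 19. (The printed limit of 5.1 is read here as 5 followed by reference mark 1.) The SAP does not say whether the stage or the derived status is carried, or which age applies at an imputed visit.

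Protocol 5.3.1.1 gives the schedule: "Tanner Stage will be assessed at Baseline, Weeks 48, 96, 144, 192, 240 and 288/Premature Discontinuation Visit".

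**The concern.** The endpoint compares a pubertal stage with an age. When a child is no longer examined the stage becomes unknown, but age is never missing and keeps advancing. Carrying the status forward freezes a judgement made under a younger child's limit. Carrying the stage and updating age assumes that puberty stopped at the last visit. Neither gives the quantity the endpoint names, the proportion at an appropriate stage for their age at that visit.

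At stake is the LOCF Tanner proportion and its confidence interval at late visits. Children who were not examined enter that denominator, in a study whose SAP expects about 55 subjects outside Japan (SAP 4.3).

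**Working it through.** **1. How long a value can be carried.** The nominal days in the SAP 6.0 window table follow 7 × week + 1: Week 48 gives 337 and Week 288 gives 2017, both as printed, and Weeks 96, 144, 192 and 240 also match.

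- Last value at Week 48: (2017 − 337)/7 = 240 weeks, or 1680/365.25 = 4.6 years.
- Last value at Weeks 96, 144, 192 and 240: 192, 144, 96 and 48 weeks.
- With the Week 48 window (Days 296 to 379) against Day 2017: 245.9 to 234.0 weeks.
- Tanner is also assessed at premature discontinuation, so an earlier value could be carried longer. From Week 4 (Day 29) it is (2017 − 29)/7 = 284 weeks.

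The 240 weeks is therefore the maximum between scheduled visits, not an absolute bound.

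**2. Two examples.** Take a girl last assessed at Week 96, aged 13.5. Age at a later visit = 13.5 + (weeks since Week 96) × 7/365.25.

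| Visit | Age | Stage 1, status carried | Stage 1 under the SAP rule | Stage 3, stage carried and age updated |
|---|---|---|---|---|
| Week 96 | 13.5 | appropriate | appropriate | appropriate |
| Week 144 | 14.4 | appropriate | inappropriate | appropriate |
| Week 192 | 15.3 | appropriate | inappropriate | appropriate |
| Week 240 | 16.3 | appropriate | inappropriate | inappropriate |
| Week 288 | 17.2 | appropriate | inappropriate | inappropriate |

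The stage 1 girl stays appropriate past a limit she has outgrown. The stage 3 girl becomes inappropriate at Week 240 with no examination.

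**3. How often this could arise.** The documents give no age, stage or dropout distribution, so these inputs are assumptions: age at M10-870 Baseline uniform, over 5-18 or over 10-18 years; equal sexes; last Tanner visit equally likely at Weeks 48, 96, 144, 192 and 240.

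- *Age band changes.* By simulation, the applicable age band differs between last assessment and Week 288 in 49% (ages 5-18) to 68% (ages 10-18) of carried values.
- *Status changes with the stage held fixed.* For a given stage and sex only one limit matters (stage 1: 14 or 15; stages 2-3: 16 or 18; stage 4: 19). Status changes if that limit falls between age at last assessment and age at Week 288. Mean carry = (240 + 192 + 144 + 96 + 48)/5 = 144 weeks = 144 × 7/365.25 = 2.76 years. Where the relevant ages lie inside the assumed range, the probability is mean carry divided by the width of the range: 2.76/13 = 21% for ages 5-18 and 2.76/8 = 34% for ages 10-18. For stage 1 with ages 10-18, some ages that would flip lie below 10, and simulation gives about 23%. Stage 5 never fails, so it gives 0%.

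The range for stages 1-4 is thus about 21-34% of values carried to Week 288. It measures how often the age rule and the carried status disagree if the stage did not move. Whether the child had progressed is unknown.

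**The case against.** Much of the opposing case stands. The sentence that brings in LOCF also requires observed cases, so the analysis wanted here is already planned. The study has no confirmatory testing. Tanner is one of 18 descriptive endpoints in SAP 10.2 and is not named among the efficacy variables in Protocol 5.3.2. Children with a discontinuation visit should have a Tanner value from when they leave, not only from the 48-week grid assumed above. Observed cases at late visits are selective too, since they describe those who stayed.

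Three stronger readings are tempting, and the documents do not support them.

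- A reader might take 49-68% as the share of wrong values. It counts age-band changes, and many of these do not alter status: a girl passing 16 at stage 4, or any child at stage 5, is classified as before.
- A reader might infer that the direction of error is a coin toss between two equal readings. SAP 6.0 carries the last value of the efficacy variable, and that variable is being at an appropriate stage, so carrying the status is more natural. The SAP nowhere describes re-ageing a carried stage. Its rule that imputes components first covers composite scores built from subscores and does not settle the matter.
- A reader might conclude that the trial cannot support any statement on maturation. Such a statement can rest on observed cases.

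Protocol 8.1.4 confines LOCF to the last visit. That does not remove the problem, because a Week 48 value carried to Week 288 is the longest carry between scheduled visits.

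**Conclusion.** The point holds as a minor one. Followed as written, the SAP produces an LOCF Tanner proportion with a confidence interval in which unexamined, ageing adolescents keep a status judged at a younger age, for up to 240 weeks from a scheduled Week 48 visit and longer from an earlier discontinuation visit. Under the assumptions in step 3, the status with the stage held fixed would change in about 21-34% of values carried to Week 288 for stages 1-4 and in none for stage 5.

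Those percentages are shares of carried values, not of all subjects. The shift in the reported proportion cannot be computed from the documents. Nothing outside the LOCF Tanner summary is affected.

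**What to change.** In SAP 10.1 or 10.2, exempt the Tanner endpoint from LOCF. State that it is analysed as observed cases, that status is evaluated at the subject's age at the actual assessment, and that the number assessed is shown at each visit.

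This costs one sentence and removes one table, and no collected data are lost. The downside is a smaller number at late visits, with a result that describes only subjects still being assessed. A footnote to the table should say so.

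If the LOCF summary is kept, the SAP should at least state whether stage or status is carried, which age applies at an imputed visit, and a maximum carry time. That would settle the ambiguity but would still report a status for children who were not examined.

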10.2 Efficacy Analysis

The efficacy endpoints are:

- The proportion of subjects who achieve clinical remission as measured by PMS (defined as a PMS ≤ 2 and no individual subscore ≥ 1) over time;
- The proportion of subjects who achieve clinical response as measured by PMS (defined as a decrease in PMS ≥ 2 points and ≥ 30% from Study M11-290-Baseline) over time;
- The proportion of subjects who achieve PUCAI remission (defined as < 10) over time;
- The proportion of subjects who achieve PUCAI response (defined as a decrease in PUCAI ≥ 20 points from Study M11-290-Baseline).
- Change from Baseline in total IMPACT III Quality of Life score and subscores over time for subjects at least 9 years old at Baseline;
- Change from Baseline in WPAI scores over time;
- Change from Baseline in "z" scores for height over time;
- Change from Baseline in BMI over time;
- Change from Baseline in "z" scores for weight-for-age over time;
- Change from Baseline in albumin and total protein over time;
- Change from Baseline in hemoglobin, hematocrit, red blood cell count over time;
- Change from Baseline in hs-CRP levels over time;
- Proportion of subjects at appropriate Tanner stage (see Section 6.0) over time;
- Proportion of subjects in Mayo score clinical response over time (for subjects with available Mayo score);
- Proportion of subjects in Mayo score clinical remission over time (for subjects with available Mayo score);
- Proportion of subjects who achieve mucosal healing over time as measured by Mayo endoscopy subscore (defined as ≤ 1, for subjects with available Mayo score)
- Proportion of subjects in 9 point Mayo score (without PGA) clinical remission over time (for subjects with available Mayo score);

• Proportion of subjects in 6 point Mayo score (without PGA and endoscopy subscore) clinical remission over time (for subjects with available Mayo score).

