The pharmacological treatment of UC in childhood is largely the same as in adulthood. Conventional pharmaceutical therapies do not completely abate the inflammatory process and have significant side effects. Conventional therapies for the induction of remission have included anti-inflammatory agents (5-aminosalicylic acid [5-ASA] derivatives and corticosteroids) and the immunomodulatory agent cyclosporine. 5-ASA derivatives as well as immunomodulatory agents (azathioprine or 6-mercaptopurine [6-MP]) have been used for the maintenance of remission. 13 Corticosteroids are not effective for the maintenance of remission. In addition to the induction and maintenance of clinical remission, absence of adverse effects on linear growth and maturation is demanded from therapy of pediatric UC. Similar to adults, corticosteroid dependence is frequent, but long-term corticosteroids are absolutely contraindicated because they do not maintain remission and have a negative effect on linear growth and bone mineralization.² Infliximab (a chimeric monoclonal anti-tumor necrosis factor [TNF]-α antibody) was approved in Europe for the treatment of pediatric patients with severe UC and in the US for the treatment of pediatric patients with moderate to severe UC based on the results of a recent study.14

The safety and efficacy of adalimumab for the induction and maintenance of clinical remission in adult subjects with moderately to severely active UC has been studied in two completed clinical trials (Study M06-826 and Study M06-827) and an ongoing open-label study (Study M10-223). In addition, adalimumab has shown clinically relevant improvements in IBDQ scores compared to placebo for up to 52 weeks in these subjects. In

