5.2.3.2 Concomitant Therapy

UC-related concomitant medication:

- Subjects who enroll into the study from blinded treatment in Study M11-290 will be allowed to change/initiate/discontinue their steroid dose after 4 weeks in Study M10-870.
- Subjects who enroll into the study from blinded treatment in Study M11-290 will be allowed to change/initiate/discontinue their azathioprine, 6-MP, MTX, 5-ASA doses after 8 weeks in Study M10-870.
- Subjects who enroll into the study from open label treatment in Study M11-290 will be allowed to change/initiate/discontinue their steroid, azathioprine, 6-MP, MTX, 5-ASA doses at any time point in Study M10-870.
- Reductions in concomitant corticosteroids, azathioprine, 6-MP, MTX, and 5-ASA will be allowed at any time in the event of moderate or severe drug-related toxicities (e.g., leukopenia, anemia, neuropathy).

Subjects may not be on both budesonide and prednisone (or equivalent) simultaneously.

Subsequent changes in all concomitant medications will be assessed at each study visit from Baseline (Week 0) through Week 288/Premature Discontinuation Visits. All subjects will be given a Subject Medication Log to help track any change in therapy. These changes will be documented in the source documents and captured on the appropriate eCRF page.

All non-UC medications (prescription and over-the-counter) used will be recorded and must include all doses and date ranges of administration. Vaccines administered to the subject will be listed as a concomitant medication. Any antibiotic used will be recorded and must include all doses and date ranges of administration.

The AbbVie Study Designated Physician identified in Section 6.1.7 should be contacted if there are any questions regarding concomitant or prior therapy(ies).

COVID-19 Pandemic - Related Vaccination Guidance

Given the ongoing COVID-19 pandemic, selected non-live vaccines (e.g., mRNA, non-replicating viral vector, protein subunit, etc.) to prevent SARS-CoV-2 infection may be administered during the study as long as components of the vaccine are not contraindicated.

The decision to receive a locally available vaccine should be based on local guidance and an individual discussion between the treating physician and the subject.

The potential impact of adalimumab on SARS-CoV-2 vaccination is unknown. Therefore, adalimumab should be given at least \pm 7 days from the SARS-CoV-2 vaccine administration.

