5.2.3.3 Prohibited Therapy

The following are prohibited medications during the study:

- Biologic therapy with a potential therapeutic impact on ulcerative colitis including but not limited to the following:
 - Anakinra (Kineret®);
 - Abatacept (Orencia[®]);
 - Natalizumab (Tysabri[®]);
 - o Efalizumab (Raptiva®);
 - Infliximab (Remicade[®]);
 - Etanercept (Enbrel®);
 - o Rituximab (Rituxan®);
 - o Tocilizumab (Actemra®);
 - o Golimumab (Simponi[®]);
 - Certolizumab (Cimzia[®]);
 - Ustekinumab (Stelara[®]);
 - o Belimumab (Benlysta®);
 - Vedolizumab (Entyvio[®]).
- The use of Tofacitinib (Xeljanz[®]) is prohibited during the study.
- Live vaccines (during the study and for 70 days after the last dose of study drug).
- The use of systemic cyclosporine, tacrolimus, or mycophenolate mofetil is prohibited during the study.
- Intravenous corticosteroid use is prohibited during the study.
- The use of investigational drugs of chemical or biologic nature are prohibited during the study.

The AbbVie study designated physician identified in Section 6.1.7 should be contacted if there are any questions regarding prohibited therapy.

- 5.3 Efficacy, Pharmacokinetic, Pharmacodynamic, Pharmacogenetic and Safety Assessments/Variables
- 5.3.1 Efficacy and Safety Measurements Assessed and Flow Chart

Study procedures will be performed as summarized in Table 1. There is a \pm 3-day window for all study visits.

Allowed protocol modifications due to states of emergency or pandemic situations are detailed in this section.

[figure not shown]

Table 1.Study Activities

Activity	Baseline (Week 0) ^a	Week 4	Week 8	Week 12	Week 24	Week 36	Week 48	Week 60	Week 72	Week 84	Week 96	Week 108	Week 120	Week 132 Call ^s
Informed Consent	X													
Inclusion/Exclusion	X													
Medical/Surgical History	X ^d													
Tobacco and Alcohol Use	X ^d													
Previous and Concomitant Medication	X ^d	X	X	X	X	X	X	X	X	X	X	X	X	X
Vital Signs ^e	X ^d	X	X	X	X	X	X	X	X	X	X	X	X	
Endoscopy (optional) ^f	X ^d						X				X			
Physical Examination ^g	X ^d	X	X	X	X	X	X	X	X	X	X	X	X	
TB testing ^h	X ^d						X				X			
Chemistry and Hematology ⁱ	X^d	X		X	X	X	X	X	X	X	X	X	X	
Urinalysis ^j	X^d	X			X		X		X		X		X	
Pregnancy Tests ^{k,l}	X ^d	X ^l	X^k	X ^l	X ^l	X ^l	X^k	X ^l	X ^l					
hs-CRP ⁱ	X ^d				X		X		X		X		X	
PUCAI	X ^d	X	X	X	X	X	X	X	X	X	X	X	X	
Partial Mayo Score	X ^d	X	X	X	X	X	X	X	X	X	X	X	X	
Mayo Score ^f	X^d						X				X			
IMPACT III Questionnaire ^m	X^d				X		X		X		X		X	

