2. PUCAI

Pediatric Ulcerative Colitis Activity Index (PUCAI) is calculated as the sum of six subscores [each being a 2 day average, see above] of PUCAI (abdominal pain [no pain = 0, pain can be ignored = 5, pain cannot be ignored = 10], rectal bleeding [none = 0, small amount with < 50% of stools = 10, small amount with most stools = 20, large amount with > 50% of stool content = 30], stool consistency of most stools [formed = 0, partially formed = 5, completely unformed = 10], number of stools per 24 hours [0 to 2 = 0, 3 to 5 = 5, 6 to 8 = 10, > 8 = 15], nocturnal stools [no = 0, yes = 10], activity level [no limitation = 0, occasionally limited = 5, severe restriction = 10]) with maximum total score 85. Higher scores represent more severe disease.

- PUCAI remission is defined as PUCAI < 10.
- PUCAI response is defined as a decrease in PUCAI ≥ 20 points from Study M11-290-Baseline.

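### Remission and response are scored without regard to on-study steroids, so the planned proportions cannot show response maintained on adalimumab without steroid rescue

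*SAP*

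**What the plan says.** **Steroid rules.** Under Protocol 5.2.3.2, subjects entering from blinded treatment in Study M11-290 "will be allowed to change/initiate/discontinue their steroid dose after 4 weeks in Study M10-870". Subjects entering from open-label treatment may "change/initiate/discontinue their steroid, azathioprine, 6-MP, MTX, 5-ASA doses at any time point in Study M10-870". No disease-activity trigger, dose ceiling, duration limit or taper is attached. Two limits apply: "Intravenous corticosteroid use is prohibited during the study" (Protocol 5.2.3.3) and "Subjects may not be on both budesonide and prednisone (or equivalent) simultaneously" (Protocol 5.2.3.2). The synopsis leaves steroids out of its bullet for open-label entrants, whereas Protocol 5.2.3.2 includes them; the two places must be reconciled.

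**Endpoints.** SAP 10.2 lists "The proportion of subjects who achieve clinical response as measured by PMS" and defines PMS response by score change only: "defined as a decrease in PMS ≥ 2 points and ≥ 30% from Study M11-290-Baseline) over time". SAP 6.0 does the same for PUCAI, for example "PUCAI remission is defined as PUCAI < 10". The Mayo, 9-point and 6-point definitions in SAP Table 2 are also built from scores only.

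**Data handling.** SAP 10.1 uses observed cases and LOCF. The non-responder imputation in Protocol 8.1.4 covers missing categorical data, not steroid use.

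**Where steroids appear in the analysis.** Baseline systemic corticosteroid use is a subgroup factor (SAP 10.5). On-study use enters only the concomitant-medication counts by generic name (SAP 7.3). SAP 10.4 leaves sensitivity analyses open.

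**The concern.** The objective in SAP 4.1 includes maintenance of clinical response on repeated adalimumab. With a single open-label group, the by-visit proportion is itself the evidence. If a child relapses, starts or increases an oral steroid and has a low score at the next visit, that visit enters the table exactly like one from a child who stayed well with no added steroid.

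The protocol gives reason to separate the two. Section 3.2 states "Corticosteroids are not effective for the maintenance of remission", and adds that steroid dependence is frequent and that long-term use harms growth. The data are also intended for a regulatory submission (Protocol 8.1.7, SAP 4.4), where readers may take the proportions as what adalimumab achieved.

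**Working it through.** The plan states no figure on this point, so there is none to reproduce. The check sets the rules side by side and then gives the scale per subject.

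**Step 1: can a steroid-recovered visit count as response?** Take a blinded-origin subject who flares between Week 48 and Week 60.

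- Protocol 5.2.3.2 permits an oral steroid start, because the subject is past Week 4.
- At Week 60 the PMS has recovered far enough to meet the response definition relative to the Study M11-290 baseline.
- SAP 10.2 contains no steroid condition, so Week 60 is a response.
- The flare may leave no trace in the visit table. If it was scored at an unscheduled visit inside the Week 60 window (Rx Days 380 to 463), SAP 6.0 keeps the assessment closest to nominal Day 421, which would usually be the scheduled visit. If the flare was scored at a scheduled visit, that visit can count as non-response; only the later, recovered visits are affected.

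**Step 2: can it be carried forward?** SAP 6.0 imputes a missing post-baseline value from the last non-missing post-baseline value. If the subject then misses Week 72, the Week 60 score fills it, and it keeps filling later visits until a new value is observed.

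**Step 3: does any other rule catch it?**

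| Provision | What it covers | On-study steroid start or increase? |
|---|---|---|
| Protocol 8.1.4, NRI | Missing categorical data | No |
| SAP 10.5, subgroup | Steroid use at Baseline | No |
| SAP 7.3, medication tables | Counts by generic name | Counted, but not linked to visit or outcome |
| SAP 8.0, dose adjustments | Adalimumab escalation, de-escalation, re-escalation | No |
| SAP 10.4, sensitivity analyses | Nothing prespecified | No |

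**Step 4: direction and scale.** With the denominator unchanged, counting steroid rescue as failure can only lower a proportion or leave it as it is. SAP 4.3 expects 55 subjects outside Japan, the population of this SAP. If k subjects are reclassified at a visit, the drop is 100 × k/55 percentage points:

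- k = 1: 100 × 1/55 = 1.8 points
- k = 5: 100 × 5/55 = 9.1 points
- k = 11: 100 × 11/55 = 20.0 points

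The values of k are for scale only. In observed-case tables with fewer than 55 subjects, each subject weighs more than 1.8 points.

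**The case against.** The strongest reply is that scoring disease activity whatever else the child receives is a legitimate treatment-policy summary. The study is descriptive, tests no hypothesis, and its title concerns long-term safety and tolerability. This stands: the current endpoints are not errors and should stay.

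Several further points also have force.

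- The protocol's defined answer to a flare is adalimumab dose escalation, with discontinuation for persistently uncontrolled disease, so steroids are not the planned rescue.
- Azathioprine, 6-MP, MTX and 5-ASA may also be started. An analysis of steroids alone does not isolate adalimumab.
- If steroids do not maintain remission, recovered scores should cluster near a course, and later scheduled visits are 12 to 24 weeks apart.
- Steroid use is not hidden: UC-related medications are tabulated. But those tables do not say whether a given remission occurred on a new steroid course.

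Three stronger readings are tempting and unsupported. A reader might attach a definite number of points to the overstatement; the documents give neither a remission rate nor a rate of steroid starts. A reader might call steroid use unrestricted; intravenous use and budesonide with prednisone are barred, and blinded-origin subjects wait 4 weeks. A reader might extend the argument to the height z-score endpoint; Protocol 3.2 says steroids impair growth, so that effect would make adalimumab look worse on height, not better.

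**Conclusion.** The point holds as a gap in what the trial can conclude. The planned proportions describe disease activity regardless of concomitant therapy and are valid as such. They do not show response maintained on adalimumab without steroid rescue, and no prespecified analysis does. The size is unknown: it depends on how many subjects start or raise systemic steroids and are then scored as in remission or response, and each such subject is worth about 1.8 points at N = 55. It would be nil if no scored remission or response coincided with steroid rescue. No error rate or power is affected, because nothing is tested.

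**What to change.** Keep the current endpoints. Add to SAP 10.2, as supportive analyses by visit:

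1. PMS remission and PMS response, counting a subject as not in remission or response if a systemic corticosteroid for UC was started, or raised above the Week 0 dose, since the previous scheduled visit, or if such a rescue course is still ongoing at the visit. An unchanged or tapering Week 0 dose is not rescue.
2. Among subjects on systemic corticosteroids at Week 0, the proportion who are off them and in PMS remission.

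Define on-study systemic corticosteroid use from the concomitant-medication data, state how budesonide and rectal steroids are classed, and say how rescue status is handled under LOCF. State in the SAP that starts of immunomodulators or 5-ASA are not addressed. Separately, reconcile the synopsis with Protocol 5.2.3.2 on steroid changes in open-label entrants.

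No new data and no change to treatment are needed. Protocol 5.2.3.1 already records reason, dates, dose, route and frequency, and Table 1 updates medications at every visit and phone call. The cost is SAP text and some programming, since SAP 7.3 groups systemic corticosteroids only for prior and Baseline use: an on-study class, a UC-indication flag and a rule for comparing doses must be written. The supportive figure may be somewhat less favourable than the main one.
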